Chemistry panel	X	X	X	X	X	[REDACTED]	X	X	X	X	X	X	X	X	X			[REDACTED]	
Pregnancy test (serum)	X	(X)																(X): Collected pre-infusion of AMG 160.	
Urinalysis	X																		
CENTRAL LABORATORY TESTS																			
[REDACTED]																			
PK sample collection																		(X): See Table 1-5 for detailed AMG 160 PK collection schedule during treatment period.	

Abbreviations and footnotes defined on last page of table.

Table 1-1. Schedule of Activities if [REDACTED] is Initiated (Cycle 1 Only)

Study Period/Treatment Cycle	SCR ^a	Cycle 1 ^b														Infusion-free interval	Notes
		1				2				3		4					
Week ^c		1	2	3	4	5	6	8	9	10	15	17	22	23	24	29	
STUDY TREATMENT AND OTHER ASSESSMENTS/PROCEDURES																	
Imaging		(X)														(X): See Table 1-6 – assessments are cycle independent	

NOTE: This schedule of activities only applies to cycle 1. After cycle 1 day 28, there is a 1-week infusion-free interval. Then resume [Table 1-4](#) Schedule of Activities beginning in cycle 2.

AE = adverse event; C1D1 = cycle 1 day 1; CBC = complete blood count; CT = computed tomography; [REDACTED] ECG = electrocardiogram; ECHO = echocardiogram; ECOG = Eastern Cooperative Oncology Group; [REDACTED] EOI = end of infusion; IPIM = Investigational Product Instruction Manual; IV = intravenous; mCRPC = metastatic castration-resistant prostate cancer; MTD = maximum tolerated dose; MUGA scan = multigated acquisition scan; [REDACTED] PET = positron emission tomography; PK = pharmacokinetic; PSMA = prostate-specific membrane antigen; SAE = serious adverse event; SCR = screening; SFU = safety follow-up

^a All screening procedures should be performed within 28 days prior to cycle 1 day 1 dosing. **Exception: serum pregnancy testing at screening is to be performed within 7 days of initiation of investigational product for females of childbearing potential.**

- ^b All assessments on AMG 160 dosing days are performed pre-infusion. Assessments should not be performed from the infusion line. End of infusion (EOI) assessments or procedures are to be completed after the AMG 160 post-infusion flush as defined by the IPIM.
- ^c Each visit week and day is relative to day 1 of each cycle. Cycle 1 visits have a \pm 1-day window from designated time point unless otherwise specified.
- ^d **Any blood samples collected during the screening window must be collected within 28 days of cycle 1 day 1.**

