^e For the [REDACTED] in cycle 1, PK samples should be collected pre-infusion and 2, 6, 24, 48, and 72 hours after start of infusion.

^f For the [REDACTED] in cycle 1, PK samples should be collected pre-infusion and 2, 6, 24, and 48 hours after start of infusion.

^g For the [REDACTED] in cycle 1, PK samples should be collected pre-infusion and 2, 6, 24, 48, 72, 96, and 120 hours after start of infusion.

Table 1-6. Schedule of Imaging Assessments (Cycle Independent)

	SCR	Treatment Period ^a		EOT	SFU	LTFU	Notes
MRI brain	X						All subjects must have MRI of the brain performed within 28 days prior to the first dose of AMG 160. All brain scans on protocol are required to be MRI unless MRI is contraindicated, then CT with contrast is acceptable. Subsequently, MRI brain can be performed at any time if clinically indicated per standard of care.
CT/MRI and tumor burden assessment (chest, abdomen and pelvis)	X	Weeks 1-24 Every 8 weeks	Weeks 25+ Every 8 weeks	X	X	X ^b	Radiologic imaging (CT/MRI) is required at the EOT or SFU visit if the subject has not had radiologic imaging performed within 6 weeks of the visit.
⁶⁸ Ga-PSMA-11 PET/CT	X	At week 8 and week 16		X			

CT = computed tomography; EOT = end of treatment; ⁶⁸Ga = 68-Gallium; [REDACTED]; LTFU = longterm follow-up; MRI = magnetic resonance imaging; PET = positron emission tomography; PSMA = prostate-specific membrane antigen; RECIST = Response Evaluation Criteria in Solid Tumors; SCR = screening; SFU = safety follow-up;

^a Timing is based on first dose of AMG 160 (cycle 1 day 1) ± 7 days for imaging assessments.

^b For subjects who discontinued treatment for any reason other than confirmed disease progression, every effort should be made to perform radiographic imaging (CT/MRI) of the chest, abdomen, pelvis, and all other known sites of disease every 3 months until documentation of confirmed disease progression per modified RECIST 1.1, clinical progression, start of new anticancer therapy, or up to 3 years after the first dose of AMG 160, whichever occurs first.

2. Introduction

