8.1 General Study Periods

8.1.1 Screening, Enrollment and/or Randomization

Informed consent must be obtained before completing any screening procedure (standard of care radiographic assessments performed before signing of informed

consent may be used for screening purposes if performed within 28 days of subject enrollment) or discontinuation of standard therapy for any disallowed therapy. After the subject has signed the informed consent form, the site will register the subject in the IRT and screen the subject in order to assess eligibility for participation. The screening window is up to 28 days. **Any blood samples collected during the screening window must be collected within 28 days of cycle 1 day 1.**

For a subject to be eligible for study participation, detectable PSMA expression by ⁶⁸Ga-PSMA-11 PET/CT imaging [REDACTED]

[REDACTED] must be demonstrated during screening. [REDACTED]

All screening evaluations must be completed and reviewed to confirm that potential subjects meet all eligibility criteria. The investigator will maintain a screening log to record details of all subjects screened and to confirm eligibility or record reasons for screening failure, (see Section 5.4) as applicable.

If a subject has not met all eligibility criteria at the end of the screening period, the subject will be registered as a screen fail. Screen fail subjects may be eligible for re-screening 1 time.

Rescreen subjects must first be registered as screen failures in IRT and subsequently registered as resccreens. Once the subject is registered as rescreened, a new 28 day screening window will begin. Subjects will retain the same subject identification number assigned at the original screening. If the rescreening period begins more than 30 days after the original signing of the informed consent form, all screening procedures, including informed consent, must be repeated.

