5.1.2 Secondary Endpoints Definitions

Objective Response (OR) per RECIST 1.1:

Objective Response is defined as a best overall response ([Appendix C](#)) of either Complete Response (CR) or Partial Response (PR) per RECIST 1.1. Radiographic response (Complete Response, Partial Response) requires confirmation by a repeat, **evaluable** scan at least 28 days after the first documentation of response.

Subjects who do not experience a PR/CR or do not have any follow-up tumor assessments will be regarded as non-responders.

Overall Survival (OS):

Overall survival is defined as the time from the date of Study Day 1 until death due to any cause:

$$\text{OS time (Days)} = \text{date of death} - \text{Study Day 1} + 1.$$

Any subject not known to have died at the time of analysis will be censored based on the last recorded date on which the subject was alive.

Duration of Response (DOR):

The duration of response is defined as time from first evidence of CR or PR to disease progression or death due to any cause, whichever occurs first. DOR will be calculated only for subjects who achieve a best overall response of PR or CR.

$$\text{DOR (months)} = (\text{PD / death date} - \text{response start date} + 1) \times 12 / 365.25$$

The time of the initial response will be defined as the earliest of the dates contributing towards the first visit response of PR or CR.

- For confirmed responders whose PR or CR are confirmed in two **evaluable** assessments, the first PR/CR assessment among the two **evaluable** assessments will be used to calculate DOR.
- For unconfirmed responders awaiting follow-up confirmation scans, the PR or CR assessment that is awaiting confirmation scan will be used to calculate DOR.

Censoring rules for Duration of Response (DOR):

- Data for responders who are alive and without disease progression or new anti-cancer therapy are censored at the time of last **evaluable** tumor assessment **by CT/MRI scan**.
- Data for responders who are alive and without disease progression but who start new anti-cancer therapy are censored at the time of last **evaluable** tumor assessment **by CT/MRI scan** before the start of new anti-cancer therapy.
- Data for responders who die or have disease progression after two or more missed evaluable tumor assessments are censored at the time of last evaluable tumor assessments **by CT/MRI scan** before the two or more missed evaluable tumor assessments.

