Appendix E. Censoring Rules

Censoring rules for PFS or TTP (radiographic):

Situation up to DCO/EOS	Date of Event or Censoring	Outcome
No evaluable post-baseline or on-study disease assessment; On study without PD or death	Date of the first dose of investigational product (AMG 160)	Censored
PD prior to new anti-cancer therapy	Date of PD	Event
No PD, but death recorded without new anti-cancer therapy	PFS: Date of death; TTP: Date of last evaluable radiographic tumor assessment	PFS: Event; TTP: Censored
Start of new anti-cancer therapy prior to PD or death, or prior to any other disease assessment if there is no PD or death recorded	Date of last evaluable radiographic tumor assessment prior to the start of new anti-cancer therapy	Censored
No PD or death, no new anti-cancer therapy	Date of last evaluable radiographic tumor assessment	Censored
Death or PD immediately after more than one consecutively missed tumor assessment**	Date of last evaluable radiographic tumor assessment prior to the missing assessments*	Censored

DCO: data cutoff; EOS: end of study; PD: progressive disease

* This supersedes the previous rules that result in Event at date of PD or death

**Implementation details: censoring with death or PD immediately after more than one consecutively missed tumor assessment

Scenarios of PD or Death	Censoring Rule	X Days in Censoring Rule
While on treatment	If PD or death is X days after the last scan, censor at the last scan	119

Censoring rules for Duration Of Response (CT/MRI assessment):

Situation up to DCO/EOS	Date of Event or Censoring	Outcome
PD prior to new anti-cancer therapy	Date of PD	Event
No PD, but death recorded without new anti-cancer therapy	Date of death	Event
Start of new anti-cancer therapy prior to PD or death, or prior to any other disease assessment if there is no PD or death recorded	Date of last evaluable tumor assessment by CT/MRI prior to the start of new anti-cancer therapy	Censored
No PD or death, no new anti-cancer therapy	Date of last evaluable tumor assessment by CT/MRI	Censored
Death or PD immediately after more than one consecutively missed tumor assessment**	Date of last evaluable tumor assessment by CT/MRI prior to the missing assessments*	Censored

DCO: data cutoff; EOS: end of study; PD: progressive disease

* This supersedes the previous rules that result in Event at date of PD or death

**Implementation details: censoring with death or PD immediately after more than one consecutively missed tumor assessment

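### The 119-day missed-scan cut-off in SAP Appendix E allows for one imaging window instead of two, so some PFS, TTP and DOR events after a single missed scan can be censored

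*SAP*

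**What the plan says.** The written rule appears twice. SAP 5.1.2 states for DOR: "Data for responders who die or have disease progression after two or more missed evaluable tumor assessments are censored". SAP Appendix E, in the tables for radiographic PFS/TTP and for DOR, censors "Death or PD immediately after more than one consecutively missed tumor assessment" and adds that this row overrides the rows that would otherwise make the case an event.

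Under each table, an implementation note turns the rule into a day count: "If PD or death is X days after the last scan, censor at the last scan", with X = 119. The only scenario listed is "While on treatment". No operator (> or ≥) is given.

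The scan dates come from Protocol Section 1.3. Table 1-6 sets CT/MRI every 8 weeks, both up to week 24 and after it, and footnote a says: "Timing is based on first dose of AMG 160 (cycle 1 day 1) ± 7 days for imaging assessments". For the baseline scan, the footnotes to the cycle 1 tables say: "All screening procedures should be performed within 28 days prior to cycle 1 day 1 dosing". After treatment ends for a reason other than confirmed progression, Table 1-6 footnote b asks for imaging "every 3 months until documentation of confirmed disease progression per modified RECIST 1.1".

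**The concern.** The day count is meant to stand in for the written rule, so it should censor a gap that contains two missed scans and keep one that contains a single missed scan. It leaves room for one scan to move within its window, while both scans bounding the gap can move. A subject who misses one scan and is otherwise inside every protocol window can therefore be treated as having missed two. Because the row overrides the event rows, nothing later in the plan restores the event.

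Radiographic PFS, TTP and DOR are named secondary endpoints in a study of up to 50 subjects plus up to 20 backfill subjects. With numbers of that size, a few reclassified events can move a Kaplan-Meier median.

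**Working it through.** **Inputs.** Interval 56 days and window ± 7 days, each scan anchored on first dose (Protocol Table 1-6 and its footnote a). Baseline scan B = 0 to 28 days before first dose (footnotes to Tables 1-1 to 1-3). X = 119 (SAP Appendix E).

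**The plan's figure.** 2 × 56 + 7 = 119: two intervals and one window.

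**Last scan is post-baseline (PFS, TTP, DOR).** With m missed scans, gap = (m + 1) × 56 + (u2 − u1), where u1 and u2 are the offsets of the two bounding scans, each from −7 to +7.

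| Missed scans | Shortest | Nominal | Longest |
|---|---|---|---|
| 0 | 42 | 56 | 70 |
| 1 | 98 | 112 | 126 |
| 2 | 154 | 168 | 182 |

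For progression found at a scan, censoring when the gap exceeds any value from 126 to 153 separates one miss from two. The value 119 lies inside the one-miss range.

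*Share affected.* Assume offsets uniform over whole days, giving 15 × 15 = 225 pairs. A gap above 119 needs u2 − u1 ≥ 8, which holds for 7 + 6 + 5 + 4 + 3 + 2 + 1 = 28 pairs, so 28/225 = 12.4%. In continuous time, (7²/2)/14² = 24.5/196 = 12.5%. If the operator is ≥, the 8 pairs with a difference of exactly 7 are added: 36/225 = 16.0%.

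*Deaths.* After a last scan at offset u1, the second following window closes 112 + 7 − u1 days later. For u1 = −7 that is 126 days, so a death at 120 to 126 days would be censored before a second assessment could be called missed.

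**Only the baseline scan precedes the event (PFS, TTP).** If the baseline scan is the last scan, week 8 is missed and progression is found at week 16, then gap = B + 112 + u2.

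- Range: 0 + 112 − 7 = 105 to 28 + 112 + 7 = 147 days. Two missed scans give at least 3 × 56 − 7 = 161.
- Week 16 scan on time: B + 112 > 119 whenever B ≥ 8.
- With B uniform over 0 to 28 days and u2 uniform (assumptions), there are 29 × 15 = 435 combinations, of which 120 have B + u2 ≤ 7. The share censored is 315/435 = 72.4%.
- Baseline 28 days early: a death from 120 − 28 = 92 to 119 days after first dose is censored while the week 16 window is still open.
- Censoring at that scan gives a date before Study Day 1, where PFS and TTP begin.
- Counted from Study Day 1 instead, the longest one-miss gap is 112 + 7 = 119, so a test of > 119 fits exactly.

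Protocol 8.1.1 also lets standard-of-care scans serve for screening: "consent may be used for screening purposes if performed within 28 days of subject enrollment". Section 5.3 allows up to 7 days from enrollment to first dose, so B could reach 35 and the longest one-miss gap 35 + 112 + 7 = 154.

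**Off treatment.** Taking 3 months as 91 days (an assumption), one missed scan gives 2 × 91 = 182 days. Appendix E gives no X for this period.

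**The case against.** The strongest defence is that 119 is built from the schedule and works for most single misses. That stands. At nominal timing one missed scan gives 112 days, and the offsets must differ by more than 7 days in the unfavourable direction before the cut-off is crossed. A reader might infer that events after one missed scan are censored in general; the arithmetic does not support that.

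A reader might also carry the early baseline scan over to DOR. It cannot matter there, because a responder has a post-baseline scan. DOR is exposed only at 120 to 126 days.

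On PFS and TTP, the defence says that baseline is not a last scan at all. Appendix D requires an evaluable assessment to yield a visit response, which a baseline scan does not have, and the SAP's habit when no post-baseline scan exists is to use first dose (the first row of the PFS/TTP table and the time-to-response definition). This is a fair reading, so the 72% is conditional on the other one. It does not close the gap: that first row is limited to subjects without progression or death, so the SAP names no reference date for exactly these events.

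Reusing 119 after treatment would censor after a single missed 3-monthly scan, but the SAP labels the value as on treatment and nowhere says to reuse it. What is left is a missing value.

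Finally, extra scans for deterioration or to confirm response (Protocol 8.2.2) can shorten gaps, and these endpoints are descriptive with no hypothesis test. Both points limit the consequence; neither makes the day count match the rule.

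**Conclusion.** The day count contradicts the rule it implements over a narrow, protocol-compliant range. On treatment, with a post-baseline last scan, PFS, TTP and DOR events 120 to 126 days after that scan can be censored although only one assessment was missed. That is about 12% of progressions found after exactly one missed scan (16% if the test is ≥), assuming scan days uniform in the window. It is not a share of all events: the documents give no missed-scan frequency, so no overall effect can be stated.

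For PFS and TTP there is a further ambiguity when only the baseline scan precedes the event. If its actual date is used, progression at an on-time week 16 scan is censored whenever baseline was 8 or more days early, and at a date before Study Day 1.

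It is tempting to conclude that PFS and DOR are lengthened. That is not established. Dropping a late event can raise the curve, but censoring early also shrinks the risk sets in between. Take 10 subjects, 5 progressing at week 8 and 5 at week 16: survival at week 8 is 0.50. Censor one of the week 16 subjects at day 1 and it becomes 4/9 = 0.44, which is lower.

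**What to change.** In SAP Appendix E, for PFS/TTP and DOR, define the condition as two consecutive scheduled assessments with no evaluable scan inside their Table 1-6 windows. This is the cleaner option because it also handles deaths exactly.

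If a day count is kept:

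- While on 8-weekly imaging with a post-baseline last scan, censor when the event is > 126 days after it (2 × 56 + 2 × 7).
- For PFS/TTP with no post-baseline scan before the event, censor when it is > 119 days after Study Day 1, with the censoring date at Study Day 1.
- State the operator (>).

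One limit of the 126-day count should be accepted knowingly. After a last scan taken 7 days late, the second window closes at 112 + 7 − 7 = 112 days, so a death at 113 to 126 days would count as an event although two windows had passed.

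As a secondary clarification, give a separate value for the 3-monthly off-treatment schedule and say whether the ± 7-day window applies there.

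The cost is SAP wording and one derivation change, with no new data. A few more events would be counted.
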